# 2. Study Objectives

# 2.1 Primary Objective

The primary objective of this non-inferiority trial involving immunologically low-risk patients is to show that the GFR 12 months post-randomization is the same for patients who receive belatacept at q-4 and q-8 dosing intervals.

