# 3. Assessment of Efficacy

### 3.1 Primary Outcome Measure

This study will compare the primary outcome of mean eGFR between the standard q-1M control group and the q-2M treatment group, with the hypothesis that mean eGFR will not vary between the groups by more than a pre-specified acceptable difference, or equivalence margin. Difference in eGFR between the q-1M and q-2M treatment groups will be assessed monthly.

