# 8. Study Population

The trial population consists of adults ≥18 years of age who are first-time transplant recipients of either living donor or deceased donor renal transplants. Patients of all races and ethnicities will be included.

This is an intention to treat, randomized, controlled trial. There will be a total of 166 subjects, randomized in equal numbers, 83 patients in each arm. We anticipate needing to consent/enroll 200 patients to achieve 166 randomized subjects accounting for an approximate 15% screen failure rate. All patients will be actively followed in the study for 12 months following enrollment. The study is projected to last 2 years.

Before any study procedures are performed, the details of the study will be described to subjects, and they will be given a written informed consent document to read. Patients who consent to participate in the study will sign and date the informed consent document in the presence of study personnel. Only patients who have given informed written consent will be included in this study.

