The mean eGFR at one year post-transplant for patients receiving belatacept at the Emory Transplant Center has been found to be 60.2 ml/min/1.73 m² with a standard deviation of 14.5 ml/min/1.73 m². When patients with an eGFR less than or equal to 35 ml/min/1.73 m² are excluded, the mean eGFR at one year post-transplant has been found to be 61.5 ml/min/1.73 m² with a standard deviation of 13.1 ml/min/1.73 m². Based on this inclusion criterion, the table below details several scenarios of potential sample size for different equivalence margins in order to attain 80% power for a significance level (alpha) of 0.05.

Calculated GFR is a continuous variable and will be assessed at monthly intervals (increasing to every two weeks from week 4 to 16 in the q-2M group) throughout the study. The secondary time points of rejection, death, graft lost, and HLA antibody production will be assessed at 6 and 12 months. Total cost, clinic visits, hospitalizations, biopsies and patient satisfaction will be assessed at 12 months.

Assuming a standard deviation of 13.1 ml/min/1.73 m^2:

Equivalence margin	N per group	Sample Size (total
(ml/min/1.73 m  )		N)
5.0	119	238
5.5	98	196
6.0	83	166
6.5	71	122
7.0	61	122

For example, assuming the standard deviation for eGFR at one year post-transplant is 13.1 ml/min/1.73 m^2, 166 patients total (83 per treatment group) are required to be 80% sure that a

two-sided 95% confidence interval will exclude a difference in mean eGFR between the treatment groups of more than 6.0 ml/min/1.73 m^2.

This study also aims to compare the secondary outcome of acute rejection rate between the q-1M and q-2M dosing interval groups. The one-year post-transplant acute rejection rate among patients treated with belatacept is expected to be 1-2%; based on this assumption, the table below details several scenarios of potential sample size for absolute differences in acute rejection rate in order to attain 80% power for a significance level of 0.05.

AR rate for reference group	AR rate for intervention group	Absolute difference	N per group	Sample Size
(q-4)	(q-8)	difference		(total N)
1%	4%	3%	137	274
1%	5%	4%	77	154
1%	6%	5%	49	98
1%	8%	7%	25	50
2%	5%	3%	270	540
2%	7%	5%	97	194
2%	8%	6%	68	136
2%	9%	7%	50	100

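### Under the plan's equivalence wording, 83 per arm gives 80% power with a two-sided 90% CI but only about 67% with the two-sided 95% CI that section 10 names

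*Combined protocol and SAP*

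**What the plan says.** The sample-size part of section 10 introduces its table as giving "several scenarios of potential sample size for different equivalence margins in order to attain 80% power for a significance level (alpha) of 0.05". With SD 13.1 ml/min/1.73 m², the table lists 119, 98, 83, 71 and 61 per group for margins of 5.0, 5.5, 6.0, 6.5 and 7.0. The trial uses the 6.0 row. The sentence under the table ties the 83 per group, and an 80% chance of success, to this criterion: "two-sided 95% confidence interval will exclude a difference in mean eGFR between the treatment groups of more than 6.0".

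The hypothesis is described in two ways:

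- Section 3.1, repeated in section 10, is equivalence: "mean eGFR will not vary between the groups by more than a pre-specified acceptable difference, or equivalence margin".
- Section 2.1 is non-inferiority: "The primary objective of this non-inferiority trial involving immunologically low-risk patients". The same sentence then sets the aim of showing that GFR is the same in the two arms.

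Section 10 assigns the 12-month eGFR comparison to a two-sample t-test of whether the mean difference is statistically significant. It also defines power as the chance of detecting a difference at least as large as the margin.

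On attrition, section 8 says only: "We anticipate needing to consent/enroll 200 patients to achieve 166 randomized subjects accounting for an approximate 15% screen failure rate".

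**The concern.** An alpha of 0.05 can mean two things in an equivalence design. It can be 5% for each of two one-sided tests, which corresponds to a two-sided 90% CI lying inside the margin. Or it can be 5% across both sides, which corresponds to a 95% CI. The second is stricter and needs more patients. The table and the sentence beneath it appear to use different conventions, so the 80% may not belong to the interval named.

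The stated power of the primary comparison is at stake, and so is the success rule. If the hypothesis and the CI level are both left open, the choice could be made after the data are seen, with a one-sided error rate of either 5% or 2.5%.

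**Working it through.** **Inputs.** SD 13.1, margin 6.0, power 80%, alpha 0.05 and 83 per arm with equal allocation come from sections 8 and 10. The true difference is taken as 0. The plan gives no number for it, but this matches the section 2.1 aim and is needed to reproduce the table.

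**Step 1: reproduce the table.** For equivalence with true difference 0, the normal approximation is

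n per arm = 2 × [SD × (z(1−a) + z(0.90)) / margin]², where a is the one-sided level of each test. The term z(0.90) arises because the 20% type II error is split between the two sides.

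- a = 0.05 (90% CI): 2 × [13.1 × (1.645 + 1.282) / 6.0]² = 81.6, so 82.
- a = 0.025 (95% CI): 2 × [13.1 × (1.960 + 1.282) / 6.0]² = 100.2, so 101.

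The exact calculation replaces z by t on 2n − 2 degrees of freedom and averages over the sampling distribution of the pooled SD. The smallest n per arm with at least 80% power is then:

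| Margin | Plan | Both sides, 90% CI | Both sides, 95% CI | Lower 95% limit only |
|---|---|---|---|---|
| 5.0 | 119 | 119 | 146 | 109 |
| 5.5 | 98 | 98 | 121 | 91 |
| 6.0 | 83 | 83 | 102 | 76 |
| 6.5 | 71 | 71 | 87 | 65 |
| 7.0 | 61 | 61 | 75 | 56 |

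The 90% CI column matches the plan in every row. Neither 95% column matches in any row.

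**Step 2: power at 83 per arm, margin 6.0.** The standard error is 13.1 × √(2/83) = 2.034, and 6.0 / 2.034 = 2.95.

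| Rule | Normal approximation | Exact t | Simulation (400,000 runs) |
|---|---|---|---|
| Both sides, 90% CI | 2Φ(2.95 − 1.645) − 1 = 80.8% | 80.4% | 80.6% |
| Both sides, 95% CI | 2Φ(2.95 − 1.960) − 1 = 67.8% | 67.0% | 67.1% |
| Lower 95% limit only | Φ(2.95 − 1.960) = 83.9% | 83.5% | 83.5% |

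For both sides with a 95% CI, 101 per arm gives 79.9% and 102 gives 80.5%. At 83 per arm, the margin that this rule excludes with 80% power is 6.63, not 6.0.

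**Step 3: what result would pass.** If the observed SD is 13.1, the CI half-width is 4.02 (95%) or 3.36 (90%).

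- Both sides, 95% CI: the observed difference must be within 6.0 − 4.02 = 1.98 of zero.
- Both sides, 90% CI: within 6.0 − 3.36 = 2.64 of zero.
- Lower 95% limit only: the q-2M mean may be at most 1.98 lower, with no upper bound.

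An observed q-2M deficit of 2.3 therefore passes the 90% rule and fails both 95% rules. A q-2M mean 3 higher passes non-inferiority and fails both equivalence rules.

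**Step 4: sensitivity.** The documents give neither figure below; both are assumptions for illustration.

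| Scenario | Both sides, 90% CI | Both sides, 95% CI | Lower 95% limit only |
|---|---|---|---|
| 10% missing 12-month eGFR (75 per arm) | 74.9% | 59.2% | 79.6% |
| True q-2M deficit of 1 ml/min/1.73 m², 83 per arm | 75.2% | 61.4% | 68.6% |

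**Separate slip.** The 6.5 row prints a total of 122, but 2 × 71 = 142. The trial does not use this row.

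**The case against.** The best defence is that the 67% belongs to only one of two documented framings. Section 2.1 calls the trial non-inferiority, and the hypothesis in section 1 is directional: no loss of renal function. On that reading the two-sided 95% CI and 83 per arm give 83.5% power, more than claimed. The 95% CI also appears only once, in an illustrative sentence about sample size, and no section states it as the decision rule. The N itself is correctly computed for alpha 0.05 on each side, so the fault could be one mislabelled interval.

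The practical range is also narrow. The two equivalence rules disagree only when the absolute observed difference is between about 2.0 and 2.6. The two 95% rules disagree only when q-2M looks better by more than about 2.0.

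All of this is correct, and it means a shortage of patients has not been shown. It does not rescue the text. Sections 3.1 and 10 use equivalence wording throughout, and under it the sentence is wrong. Under non-inferiority, 83 is more than the number required. No section chooses between the readings, and the significance test that section 10 assigns to eGFR is neither kind of rule. The sensitivity figures rest on assumed inputs and carry no weight in this conclusion.

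**Conclusion.** The concern holds. The 83 per arm was derived for a two-sided 90% CI inside ±6.0, and section 10 attaches it and the 80% to a two-sided 95% CI. Under the equivalence wording, power is overstated by about 13 percentage points (67% against 80%). Under non-inferiority it is understated by about 3 points (83.5%). The primary outcome has no single stated success rule, which is why this must be fixed even though the sample size may turn out to be adequate.

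These figures rest on SD 13.1, a true difference of 0 and 83 evaluable patients per arm. The last is optimistic, because the plan's only allowance is for screen failures before randomization.

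**What to change.** State one hypothesis and one CI level for the primary analysis, and use them in sections 2.1, 3.1 and 10. In section 10 this includes the paragraph assigning a t-test of significance to 12-month eGFR and the definition of power, both of which conflict with every option below. Three options add no patients:

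- **(a) Non-inferiority, 95% CI.** This fits section 2.1 and keeps the interval already named. Suggested text: q-2M is non-inferior if the lower limit of the two-sided 95% CI for the difference in mean 12-month eGFR (q-2M minus q-1M) is above −6.0; with SD 13.1 and a true difference of 0, 83 per arm gives about 83% power, and 76 evaluable per arm (1 − 76/83, about 8% missing) gives 80%.
- **(b) Equivalence, 90% CI inside ±6.0.** Power is 80%. Say plainly that each one-sided test is at 5%, not 2.5%.
- **(c) Equivalence, 95% CI inside ±6.0.** State power of about 67%.

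Whichever is chosen, state that the power assumes a true difference of 0 and complete 12-month eGFR. Fix the rule before any between-arm comparison of 12-month eGFR. Correct the 6.5 row total to 142.

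The cost is wording and restated numbers; (b) also accepts the looser one-sided error rate. Keeping both the two-sided 95% CI equivalence rule and 80% power would need 102 evaluable per arm, that is 2 × (102 − 83) = 38 more patients.

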Belatacept immunosuppressive therapy was implemented in the Emory Transplant Center (ETC) beginning in August of 2011. Current dosing protocol requires post-transplant kidney patients who are treated with belatacept to receive an infusion every 1 month, which presents logistical challenges due to the high cost of infusions, the limited capacity of the sites administering infusions, and inconvenience to patients. Definitive clinical evidence is lacking for equivalent treatment outcomes for patients who receive infusions at one month (q-1M) intervals versus every two month (q-2M) intervals. Data from five year (Vincenti F, Blancho G, Durrbach A et al. J Am Soc Nephrol 2010) and ten year (personal communication, [name]) follow up of the phase II clinical studies suggest that there are no significant differences in the patient outcomes for q-1Mversus q-2 Mdosing intervals. However, conclusions regarding differential

outcomes for the dosing interval regimens were limited by small sample size and deserve further investigation.

We hypothesize that immunologically low risk patients who are stable on belatacept therapy at least one year post transplant can be safely transitioned from an every 1 month to an every 2 months belatacept schedule, without a decrease in renal function or an increase in acute rejection. The Emory Transplant Center is uniquely qualified to perform this every two month study. We perform approximately 230 kidney transplants per year, utilizing belatacept as standard therapy in all eligible patients (Epstein Barr Virus (EBV) positive, etc). We have performed almost 500 kidney transplants on patients using belatacept as the primary immunosuppressant medication between August 2011 and the present (May 2015). Based on this clinical volume and high rate of belatacept use, we propose to screen approximately 18 patients per month and estimate enrolling an average of 12 patients per month into the study, specifically converting 6 patients per month from a q-1 month to a q-2 month schedule.

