# 2.2 Secondary Objective

- Assessing the incidence and severity of acute rejection 6 and 12 months post randomization
- Assessing the total cost associated with q-1M and q-2M dosing intervals
- Assessing the incidence of infection in the q-1M and q-2M patient groups
- Assessing the incidence of death and graft loss at 6 and 12 months
- Assessing the incidence of human leukocyte antigen (HLA) antibodies at randomization and at 6 and 12 months
- Assessing the frequency of clinic visits, hospitalizations, and transplant biopsies in the two patient groups

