# 9. Study Procedures and Assessments

# See Appendix 3.

# 10. Statistical Analysis

All analyses will be conducted on the intent-to-treat (ITT) population. The distribution of continuous outcome measures will be examined, and non-parametric equivalents of the two-sample t-test will be used to assess the statistical significance of non-normally distributed outcomes.

Statistical significance of the mean difference in eGFR between the q-4 and q-8 treatment groups at 12 months post-randomization will be assessed using the two-sample independent t-test statistic. The incidence of clinically suspected or biopsy-proven acute rejection (and date of acute rejection) will be collected based upon final ETC biopsy-proven acute rejection. We will describe acute rejection rates at 6 and 12 months post-randomization for the overall cohort and for the q-1M and q-2M treatment groups by calculating time to acute rejection. Kaplan-Meier analyses examining time to acute rejection will be used for comparisons by treatment group, with the log-rank test used to assess statistical significance. Potential differences in the severity of acute rejection between the treatment groups will be assessed by comparing the proportions of grade IIA and lower rejections and grade IIB and higher rejections between the treatment groups. Statistical significance of acute rejection severity will be assessed using the two-sample independent t-test statistic.

The incidence of infection in the q-4 and q-8 treatment groups will be collected based on labs performed at regular intervals throughout the study duration. Differences in the incidence of infection by treatment group will be assessed using the two-sample t-test statistic. The incidence of death and graft loss will also be determined, and the death rate and graft loss rates will be calculated at 6 and 12 months post-randomization. Kaplan-Meier analyses examining time to death and time to graft loss will be used for comparisons by treatment group, with the log-rank test used to assess statistical significance.

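### The acute-rejection sample-size table does not give 80% power for the rates it labels, and its N do not match the planned log-rank test

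*Combined protocol and SAP*

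**What the plan says.** Section 10 (Statistical Analysis) introduces the rejection calculation with "This study also aims to compare the secondary outcome of acute rejection rate between the q-1M and q-2M dosing interval groups". It takes an expected first-year rate of 1 to 2% and then offers "scenarios of potential sample size for absolute differences in acute rejection rate in order to attain 80% power for a significance level of 0.05".

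The table pairs a q-4 reference rate with a different q-8 rate under the column heading "AR rate for intervention group", and adds the absolute difference, N per group and total N. The eight N per group are 137, 77, 49, 25, 270, 97, 68 and 50. Neither the table nor the text around it gives a rejection margin, says whether the 0.05 is one- or two-sided, or says that the two true rates are assumed equal.

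Earlier in the same section the analysis is named: Kaplan-Meier analyses of "time to acute rejection will be used for comparisons by treatment group, with the log-rank test used to assess statistical significance". That is a test of difference.

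Section 2.2 lists rejection first among the secondary objectives ("Assessing the incidence and severity of acute rejection 6 and 12 months post randomization"). The hypothesis in section 1 is that patients can move to the longer interval "without a decrease in renal function or an increase in acute rejection". Section 8 sets 83 patients per arm, which is the 6.0 ml/min/1.73 m² row of the eGFR table.

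**The concern.** Read as labelled, the table says that 77 patients per group give 80% power when the true rates are 1% and 5%. A test of difference with so few expected events needs far more than that: 77 × (0.01 + 0.05) is fewer than 5 events in the two arms together.

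What is at stake is how a null rejection result will be read. Five of the eight printed N (77, 49, 25, 68 and 50) lie below 83. A reader would therefore conclude that the trial has at least 80% power for those five differences, and could take a non-significant log-rank test as support for the no-increase part of the hypothesis.

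**Working it through.** **Inputs**, all from section 10 except the last: power 80%; significance level 0.05, sidedness not stated; reference rate 1% or 2%; q-8 rates as tabulated; 83 per arm with 12 months of follow-up (section 8).

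**Step 1: reproduce the printed N.** With reference rate p in both arms and the absolute difference d used as a margin,

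n = (1.645 + 0.842)² × 2p(1−p) / d².

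For 1% v 5%: 6.183 × 2 × 0.01 × 0.99 / 0.04² = 76.51, which rounds up to 77. All eight rows match in this way (column A below). Other versions fail. A one-sided 2.5% level gives 173 in row 1, and two one-sided tests with beta split give 189, against the printed 137. Using both labelled rates in the variance at one-sided 5% gives 332, 222, 164, 106, 461, 210, 161 and 129. The labelled q-8 rate therefore enters only through d.

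**Step 2: N needed to detect the labelled difference.** The pooled two-proportion formula is

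n = [z_α √(2p̄(1−p̄)) + 0.842 √(p₁(1−p₁) + p₂(1−p₂))]² / d²,

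with z_α = 1.960 (two-sided 5%) or 1.645 (one-sided 5%). For 1% v 5%, two-sided: (1.960 × 0.2412 + 0.842 × 0.2396)² / 0.0016 ≈ 284.3, so 285.

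**Step 3: power of the planned test at the printed N.** Log-rank power was simulated with exponential event times, 12 months of follow-up, no dropout and 40,000 runs per row.

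| Rates | Printed N | A: equal-rate margin | N, two-sided | N, one-sided | Log-rank power, two-sided | Log-rank power, one-sided |
|---|---|---|---|---|---|---|
| 1% v 4% | 137 | 136.02 | 424 | 334 | 34.3% | 52.5% |
| 1% v 5% | 77 | 76.51 | 285 | 224 | 28.7% | 47.8% |
| 1% v 6% | 49 | 48.97 | 211 | 167 | 21.7% | 39.8% |
| 1% v 8% | 25 | 24.98 | 137 | 108 | 11.0% | 26.2% |
| 2% v 5% | 270 | 269.28 | 588 | 463 | 48.6% | 60.9% |
| 2% v 7% | 97 | 96.94 | 269 | 212 | 37.1% | 55.3% |
| 2% v 8% | 68 | 67.32 | 206 | 163 | 34.6% | 54.0% |
| 2% v 9% | 50 | 49.46 | 166 | 131 | 33.2% | 51.2% |

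The two N columns come from the two-proportion formula. They are 2.2 times (588/270) to 5.5 times (137/25) the printed N two-sided, and 1.7 times (463/270) to 4.3 times (108/25) one-sided. Log-rank formulas give two-sided N, in table order, of 320, 200, 143, 89, 529, 223, 160 and 128 (Schoenfeld) or 440, 300, 229, 145, 600, 278, 220 and 173 (Freedman). These are rough with about 2 to 19 expected events, but every one exceeds the printed N.

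Exact enumeration of the pooled chi-square test at the printed N agrees with the simulation: 11 to 48% two-sided and 26 to 60% one-sided.

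**Step 4: power at the actual 83 per arm.**

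| Rates | Exact chi-square, two-sided / one-sided | Simulated log-rank, two-sided / one-sided |
|---|---|---|
| 1% v 5% | 30.9% / 50.9% | 31.1% / 51.1% |
| 2% v 8% | 40.6% / 60.7% | 41.5% / 60.8% |
| 1% v 8% | 61.4% / 79.7% | 61.9% / 79.8% |

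The smallest q-8 rate with 80% exact chi-square power at 83 per arm is 10.5% (v 1%) or 12.9% (v 2%) two-sided, and 8.1% or 10.7% one-sided.

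**The case against.** The strongest reply is that the table is a non-inferiority calculation and, as such, correct. The trial is described as non-inferiority, the table follows a discussion of equivalence, and a hypothesis of no increase suits a margin better than a search for a difference. The q-8 column equals reference plus difference, so it may have been meant as a limiting rate. The eGFR table also looks like an equal-means margin calculation: a normal approximation gives 81.6 for the 6.0 margin, against the printed 83.

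This is a likely account of where the numbers came from, and it makes the fault one of labelling and alignment rather than arithmetic. It does not clear the plan. The eGFR table has a column for its margin; the rejection table has two arm rates instead. No rejection margin or one-sided level appears anywhere. The planned log-rank test of difference would not exclude a margin even if one were stated.

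The second reply is that little follows: rejection is secondary, no row is chosen, and no sentence claims power for rejection at 83 per arm. The enrolment-review thresholds in section 4.4 do not use this table either. All of this is true and limits the weight of the point. The largest ratios also come from the 1% v 8% row at 25 per arm, a size nobody proposed; at 83 per arm that row has about 80% power one-sided. The figures at 83 per arm are the ones that matter.

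**Conclusion.** The concern holds. The table states 80% power for labelled pairs of rates, and no printed N delivers it for the planned test under either sidedness. The shortfall does not depend on how the N were obtained; that they came from an equal-rate, one-sided 5% margin formula is an inference from eight exact matches. At 83 per arm the trial has 31% (two-sided) or 51% (one-sided) power for 1% v 5%, and 41% or 61% for 2% v 8%. These figures take the labelled rates as true and assume no dropout; the log-rank figures also assume exponential event times. The point should be fixed, but it touches a secondary outcome only: neither the 166 patients nor the primary analysis is affected.

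**What to change.** Choose one reading and make the table and the analysis agree.

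- **If a margin was meant:** relabel the columns as common true rate and non-inferiority margin, state the chosen margin and the one-sided level, and analyse rejection with a named confidence interval for the rate difference. Compute power for that interval, because the normal formula is unreliable at 1 to 2 expected events per arm. With 83 per arm at one-sided 5%, a 1% rate and a 4-point margin give 51.5% power (Newcombe) to 82.9% (Wald), where the formula gives 82.8%. A 2% rate and a 6-point margin give 75.5% to 84.6%, where the formula gives 86.8%.
- **If a difference was meant:** keep the log-rank test, state its sidedness, and replace the table with true power at 83 per arm.

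Under either reading, report the rejection-rate difference with its 95% CI. That is good practice rather than part of the repair, but it shows directly what size of increase the data exclude.

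The cost is one table and a few sentences, and a less favourable statement of power for rejection.
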